6 ANALYSIS POPULATIONS

The primary analyses of the data will be based on the safety population (SAF). Supportive analyses of the efficacy data will be performed on a per-protocol (PP) population.

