6.2 PER-PROTOCOL POPULATION

The PP population will consist of those patients who receive telotristat etiprate and have no major protocol deviation(s) that would interfere with the collection or interpretation of the efficacy data. Patients with significant protocol deviations will be excluded from the PP population. Determination of the PP population will be made before database lock. The primary analyses of efficacy will be based on the SAF; the PP population will be used in a supplemental manner.

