6.3 SAFETY POPULATION

The SAF consists of all patients receiving any fraction of a dose of telotristat etiprate during the study.

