8.2 PROTOCOL DEVIATIONS

Protocol deviations will be captured during monitoring visits. Before database lock, the study Sponsor will review all protocol deviations and determine whether or not they are significant protocol deviations. Additional deviations may be identified through programmatic check or during clinical review of the data.

Significant protocol deviations include, but are not limited to, the following:

- Patient did not meet all inclusion or met any of the exclusion criteria
- Patient's study drug compliance rate was <75%

All significant protocol deviations by treatment group will be listed.

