8.6 EFFICACY

Analyses of the efficacy data will be performed on the PP population, and the analysis will be applied to the QoL measures, adequate relief of CS symptoms, subjective global assessment, and plasma 5-HIAA values. Majority of patients enrolled in this study may have progressive disease, and their symptoms (not governed by inhibition of serotonin synthesis) may get worse due to disease progression.

The primary analysis will be based on the observed data and missing data will not be imputed, unless stated otherwise for specific analyses. All efficacy and pharmacodynamic variables (plasma 5-HIAA) will be summarized descriptively per study visit as the actual outcomes and change from Baseline scores where applicable, and listed.

Statistical tests and estimates of within patient effects for these measures will be derived from application of a mixed model with repeated measures (MMRM). The model will be generalized to handle missing data and specific to the measurement properties of the dependent variables. Non-parametric methods will be used to supplement the tests and estimates from the mixed linear model. Analysis of efficacy endpoints will be made using statistical tests each with a 2-sided α -level = 0.05.

8.6.1 Change from Baseline in Overall and Domain Scores of the EORTC QLQ-C30 and GI.NET21 at Each Study Visit

The EORTC QLQ is an integrated system for assessing the health related QoL of cancer patients participating in international clinical trials. The QLQ-C30^[2] version 3.0 is composed of both multi-item scales and single-item measures. These include 5 functional scales (physical functioning, role functioning, emotional functioning, cognitive functioning, and social functioning), 3 symptom scales (fatigue, nausea and vomiting, and pain), a global health status / QoL scale, and 6 single items (dyspnea, insomnia, appetite loss, constipation, diarrhea, and financial difficulties). All of the

Statistical Analysis Plan

scales and single-item measures range in score from 0 to 100. A high scale score represents a higher response level.

For all scales, the *RawScore*, *RS*, is the mean of the component items:

$$RawScore = RS = (I_1 + I_2 + \dots + I_n) / n$$

Then for functional scales:

$$Score = \left\{ 1 - \frac{RS - 1}{range} \right\} \times 100$$

And for symptom scales / items and global health status /QoL:

$$Score = \{(RS - 1) / range\} \times 100$$

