The change from Baseline in overall and each domain score of EORTC QLQ-C30 and GI.NET21 at each study visit will be analyzed using a MMRM for the PP population. The model will use the change from Baseline in overall or each domain score of EORTC QLQ-C30/GI.NET21 as the dependent variable and will include a fixed effect of time (Baseline Day 1 up to Week 84/EOS). The Baseline QLQ-C30/GI.NET21 value will be included in the model as a covariate. The Kenward-Roger approximation will be used to adjust the denominator degrees of freedom. A first-order heterogeneous autoregressive covariance structure will be assumed initially to model the within-patient errors; however, other covariance structures will be tested and may be used in the final model if a better fit is evident. The least squares (LS) means, 95% 2-sided CLs, and the p-values of LS means at each visit will be reported to evaluate the within-patient treatment effect. The null hypothesis is that there is no treatment effect (no difference from Baseline values) over time. A sample SAS code for the model is shown below.

*USUBJID: unique patient ID
AVISITN: analysis visit (e.g., week 24, week48, week 72 and week 84)
RESP: non-count data (e.g., change from Baseline in Global health status/QOL score)
BASE: non-count data (e.g., Baseline Global health status/QOL score);

```
ods output lsmeans=estimates;  
proc mixed data=adeft method=reml;  
  class USUBJID AVISITN;  
  model RESP = AVISITN BASE / ddfm=kr;  
  repeated AVISITN / subject=USUBJID type=ARH(1);  
  random intercept / subject=USUBJID;  
  lsmeans TRT01PN*AVISITN / cl;  
run;  
ods output close;
```

Friedman's nonparametric method for testing treatment group differences will be used to supplement the MMRM. Friedman's test uses the ranks of the data rather than their raw values to calculate the statistic, and the test does not make a distribution assumption of the data. The null hypothesis of the test is that the change from Baseline in Global health status/QOL score are the same over time, and the alternative hypothesis is that the change from Baseline in Global health status/QOL score are different over time. Friedman's test cannot handle missing data, so patients with incomplete measurements will be dropped when applying Friedman's test. A sample SAS code for the model is shown below.

*USUBJID: unique patient ID
AVISITN: analysis visit (eg, week 24, week48, week 72 and week 84)
RESP: change from Baseline in Global health status/QOL score;

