16 APPENDICES

Attachment 1: Table shells

Attachment 2: Listing shells

Attachment 3: Figure shells

Note to File

Subject: Addendum to Statistical Analysis Plan for Studies LX1606.301, 302, 303, and for the LX1606 Integrated Safety Summary (ISS)

RE: Calculation of Extent of Exposure for Open Label Phases of Studies LX1606.301 and LX1606.303, and Study LX1606.302, and in the LX1606 ISS

Date: November 3, 2015

CC: Lexicon- [REDACTED]
[REDACTED] INC- [REDACTED] Ipsen- [REDACTED]
[REDACTED] InStat Services: [REDACTED]

Background:

This note to file is intended to document the methodology to be used in estimating duration of exposure to LX1606 in the above studies and in the ISS for the interim summaries of data which are being provided for inclusion in regulatory submissions.

Study 302 and the Extension Periods of Studies 301 and 303 The referenced studies all provide open label treatment of 500 mg tid for all patients In these studies, the electronic Case Report Form (eCRF) design includes a single page (Study Drug Accountability Extension Period; SDAEP) which records information about study drug administration during the open-label period, including first dose date, last dose date, and compliance calculation. The SDAEP eCRF is intended to be completed when the patient completes or terminates early from the study. Because many of the patients in the open-label studies are currently continuing treatment, and will not have completed SDAEP forms, it is not possible to accurately estimate study drug exposure based on these pages for such patients.

Plan:

The following approach has been agreed:

- Where the SDAEP eCRF includes both the first dose and last dose dates, the patient's duration of open label treatment exposure will be calculated using these dates. If the page also includes study drug compliance information, these patients will also be included in the reporting of study drug compliance.
- Any patient without a last dose date will have their duration of exposure estimated by using the date of the last recorded visit in the eCRF (scheduled or unscheduled), up to and including the week 48 visit (ie, excluding Follow Up visits). The time on study drug will be estimated for these patients, but no estimation will be performed that includes study drug compliance, dose, or amount of drug received during the study.

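### Sections 6 and 6.2 make the safety population primary for efficacy, but Sections 8.6 and 8.6.1 specify the efficacy analyses on the per-protocol population only

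*SAP*

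**What the plan says.** Four places in the SAP assign the efficacy population.

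- **Section 6 (Analysis Populations)** puts the primary analyses on the SAF and adds: "Supportive analyses of the efficacy data will be performed on a per-protocol (PP) population".
- **Section 6.2 (Per-Protocol Population)** says it for efficacy specifically: "The primary analyses of efficacy will be based on the SAF; the PP population will be used in a supplemental manner".
- **Section 8.6 (Efficacy)** opens with "Analyses of the efficacy data will be performed on the PP population" and applies this to the QoL measures, adequate relief, the subjective global assessment and plasma 5-HIAA.
- **Section 8.6.1** states that change from baseline in the QLQ-C30 and GI.NET21 scores "will be analyzed using a MMRM for the PP population".

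Sections 8.6.2 and 8.6.3 name no population.

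The SAF is every treated patient: "The SAF consists of all patients receiving any fraction of a dose of telotristat etiprate during the study" (Section 6.3). Patients with significant protocol deviations leave the PP population (Section 6.2). Section 8.2 lists two such deviations, failed eligibility and "Patient's study drug compliance rate was <75" per cent. It says that the list is not exhaustive and that the sponsor makes the classification before database lock.

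The Note to File of 3 November 2015 on extent of exposure explains when compliance becomes available: "The SDAEP eCRF is intended to be completed when the patient completes or terminates early from the study". For patients without a last dose date, that note allows time on drug to be estimated but not compliance.

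**The concern.** The section that ranks the populations and the section that specifies the analyses do not agree. A reader who starts from Section 6 expects SAF efficacy tables with PP tables in support. A programmer who starts from Section 8.6 finds PP analyses and nothing on the SAF.

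The choice matters because long-term change in QoL is the only stated secondary objective (Section 3.2), and the study has no control arm. Every efficacy result is a change within patients, so no comparator offsets a selection effect. If patients who take less than 75% of their tablets are also those who do badly, leaving them out makes the long-term course look better than it was among all treated patients. The efficacy results carry p-values, each test at a two-sided 0.05 level, and the SAP as written would let either population be presented as the one planned.

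**Working it through.** The plan gives no sample size calculation, effect size, expected exclusion rate or dropout rate, so there is no figure of its own to reproduce. The check is mainly a comparison of text.

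**Step 1. Which population does each section name for efficacy?**

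| SAP section | SAF | PP |
|---|---|---|
| 6 | primary | supportive |
| 6.2 | primary | supplemental |
| 8.6 | not named | named for all efficacy measures and 5-HIAA |
| 8.6.1 | not named | named for the repeated-measures model |
| 8.6.2, 8.6.3 | not named | not named; PP carries over from 8.6 |

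**Step 2. Does anything resolve it?** Section 12 reports no changes from the protocol's planned analysis and does not mention populations. The appended notes and memoranda deal with exposure, visit mapping, race data, missing baseline values, subject numbers and GI.NET21 scoring. None deals with the efficacy population. Section 7.1 adds that measurements from patients outside a predefined population stay out of summary tables unless otherwise specified. Followed literally, Section 8.6 therefore yields PP-only efficacy tables.

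**Step 3. What does PP select on?** Of the two listed deviations, failed eligibility is a pre-treatment criterion and compliance below 75% is post-baseline. The rest of the list is open, and treatment is open-label. Outcome summaries also existed during the study: the Note to File of 23 November 2015 records a decision taken after review of draft tables from the 16 October 2015 extraction.

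**Step 4. What happens at an interim report?** Compliance sits on a form meant for completion when a patient finishes or stops. The 75% rule can therefore remove patients who have finished or stopped, but not patients still on drug, whatever tablets they have taken. PP at an interim cut applies its main post-baseline criterion unevenly.

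**Step 5. How large could the shift be?** Let f be the share of SAF patients excluded from PP. For a crude mean change,

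mean(SAF) = (1 − f) × mean(PP) + f × mean(excluded),

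so mean(PP) − mean(SAF) = f × [mean(PP) − mean(excluded)].

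The document gives neither f nor the difference. Both are assumed here: f from 5% to 30%, and excluded patients 5 to 20 points worse on a 0-100 scale.

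| f (assumed) | PP n if SAF n = 100 | 5 points | 10 points | 20 points |
|---|---|---|---|---|
| 5% | 95 | 0.25 | 0.5 | 1.0 |
| 10% | 90 | 0.5 | 1.0 | 2.0 |
| 20% | 80 | 1.0 | 2.0 | 4.0 |
| 30% | 70 | 1.5 | 3.0 | 6.0 |

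The SAF size of 100 is the upper enrolment figure in Section 4.5. The shift runs from 0.25 to 6 points and changes sign if the excluded patients do better.

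**The case against.** The strongest defence is that primacy is not contradicted. Sections 6 and 6.2 rank the populations in plain terms, Section 8.6 never calls PP primary, and its sentence on the primary analysis and missing data names no population. On that view, Section 8.6 describes the supportive run and a careful reader would still put the SAF first. This stands in part: the defect is an omission of the primary population from the operative section, not a declaration that PP is primary. It does not remove the problem, because no SAF efficacy analysis is specified anywhere in Section 8.6 and the detailed model is assigned to PP.

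Three further limits stand.

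- PP selection is only partly post-baseline, since eligibility failures also count. Section 6.2 also confines exclusion, in its first sentence, to major deviations that affect the efficacy data, although the next sentence speaks of significant deviations without that limit.
- The illustration in points is for a crude mean. The plan reports model-based means by visit, and patients who stop early contribute little at late visits, so the share excluded at Week 72 or 84 may differ from the overall share. The points do not carry over to adequate relief, the 0-10 rating or 5-HIAA.
- Section 4.2.2 already bars patients with major deviations or tolerability concerns in the parent study, which makes the upper end of the assumed exclusion range less likely.

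**Conclusion.** The point holds. Sections 8.6 and 8.6.1 place the efficacy and 5-HIAA analyses on PP, no efficacy analysis there is assigned to the SAF, and this departs from the hierarchy in Sections 6 and 6.2. Nothing else in the SAP or its appended notes settles it.

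The size of the effect is unknown. The 0.25 to 6 points rest wholly on assumed inputs and only show that the choice of population need not be trivial. The conflict needs correcting whatever the size.

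A reader might infer more than the document supports:

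- *That PP biases change from baseline upwards.* The direction is an assumption. If excluded patients do worse, the shift is favourable, which means lower values on the QLQ-C30 symptom scales and the 0-10 rating, and lower 5-HIAA if worse means higher. Only on functional and global health scores would it be upwards.
- *That deviations were in fact classified with outcomes in view.* The open-label design and an open list permit this, but the document does not say that it happened.
- *That the study's main conclusion is at risk.* The primary objective is safety, and Section 9 reports safety on the SAF without conflict. Only the secondary QoL and symptom results and the pharmacodynamic result are affected.

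**What to change.** - In Sections 8.6 and 8.6.1, replace the PP population with the SAF for the primary efficacy and 5-HIAA analyses.
- In Sections 8.6.2 and 8.6.3, which name no population at present, state that the analyses use the SAF.
- In each of these sections, add that the analysis is repeated on PP as supportive, in line with Section 6.2.
- At any interim report, rely on the SAF and defer the PP analysis until compliance is recorded for all patients. Do not instead restrict PP to patients with recorded compliance: that would confine it to those who had finished or stopped, a stronger post-baseline selection than the 75% rule itself.

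The cost is a wording change in the SAP and, if the efficacy tables were produced on PP only, one rerun on the SAF. No new data are needed.

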7 GENERAL ASPECTS FOR STATISTICAL ANALYSIS

7.1 GENERAL METHODS

Statistical methodology and analyses are in accordance with the principles outlined by the International Conference on Harmonisation (ICH) E9 guidelines^[1].

Patient listings of all data represented in the electronic case report form (eCRF) will be provided. Measurements from patients excluded from the predefined analysis populations or extra measurements (such as unscheduled or repeat assessments) will not be included in summary tables unless specified otherwise, but will be included in the patient listings. In general, the patient listings will be sorted by treatment group,

1003157

Lexicon Pharmaceuticals, Inc.

LX1606.302

Final V1.0

Statistical Analysis Plan

patient number, and assessment date (and time), if applicable. For most summary statistics, data will be analyzed and displayed by the order of the treatment groups and overall, where treatment groups correspond to how patients were dosed on Day 1 of this study.

Unless otherwise specified, continuous/quantitative variables will be summarized using descriptive statistics, which will include the number of patients with data to be summarized (n), mean, standard deviation (SD), median, minimum, and maximum. The same number of decimal places as in the raw data will be presented when reporting the minimum and maximum, 1 more decimal place than in the raw data will be presented when reporting the mean and median, and 2 more decimal places than in the raw data will be presented when reporting the SD.

All categorical/qualitative data will be presented using frequency counts and percentages. The total number of patients in the treatment group overall (N) will be used as the denominator for percentage calculations, unless stated otherwise in the table shell. All percentages will be presented as 1 decimal point, unless otherwise specified. Percentages equal to 100 will be presented as 100%, and percentages will not be presented for zero frequencies.

All statistical tests will be 2-sided and have an associated α -level = 0.05 unless mentioned otherwise. Confidence limits (CLs) will be 2-sided and calculated with a 95% confidence coefficient.

All statistical analyses will be done using SAS statistical software version 9.3 or higher.

In the case of multiple or repeat assessments at a scheduled visit, the latest value at the visit will be used for summarization and analyses.

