8.6.3 Change from Baseline in Plasma Levels of 5-HIAA at Each Study Visit

Fasting (of at least 6 hours) blood samples, for measurement of 5-HIAA in plasma, will be collected and analyzed by a specialty laboratory based on the scheduled of visits in [Table 1](#).

The change from Baseline in plasma 5-HIAA levels will be analyzed using a MMRM. The model will use the change from Baseline in plasma 5-HIAA levels as the dependent variable, and will include patient as a random effect, Baseline plasma 5-HIAA levels as a covariate, time as fixed effect. The Kenward-Roger approximation will be used to adjust the denominator degrees of freedom. A first-order heterogeneous autoregressive covariance structure will be assumed initially to model the within-patient errors; however, other covariance structures will be tested and may be used in the final model if a better fit is evident. The LS means, a 95% 2-sided CLs and the p-values of LS means at each visit will be reported for each study visit to evaluate the treatment effect. A sample SAS code for the model is shown below.

*USUBJID: unique patient ID
AVISITN: analysis visit (eg, week 12, 24, 36, 48, 60, 72, 84 and follow-up visit)
PLA5HIAA: Baseline plasma 5-HIAA levels
RESP: non-count data (eg, change from Baseline in plasma 5-HIAA level)

```
ods output lsmeans=estimates;  
proc mixed data=adev method=reml;  
  class USUBJID AVISITN;  
  model RESP = PLA5HIAA AVISITN / ddfm=kr;  
  repeated AVISITN / subject=USUBJID type=ARH(1);  
  random intercept / subject=USUBJID;  
  lsmeans TRT01PN*AVISITN / cl;  
run;  
ods output close;
```

Lexicon Pharmaceuticals, Inc.
[name]
[name]

1003157

Lexicon Pharmaceuticals, Inc.

LX1606.302

Final V1.0

Statistical Analysis Plan

Descriptive summary statistics will be provided for the observed value and change from Baseline value of the plasma 5-HIAA levels. A graphic display of the parameter estimates and the 95% CLs for the plasma 5-HIAA levels over time will be provided.

Friedman's test for repeated measures will be used to supplement the MMRM, which is similar to that applied in Section **Error! Reference source not found.****Error! Reference source not found.**

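### Single-group LS mean changes are tested with a standard error that leaves out the sampling variance of the mean Baseline, so the limits are generally too narrow for the stated null

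*SAP*

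**What the plan says.** Section 8.6.1 takes the change from Baseline in each EORTC QLQ-C30 and GI.NET21 score as the response, with visit as the fixed effect. On Baseline it says "The Baseline QLQ-C30/GI.NET21 value will be included in the model as a covariate". The sample code reads "model RESP = AVISITN BASE / ddfm=kr". There is no treatment term and, by design, no randomised comparator.

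The inference is about each adjusted mean itself: "the p-values of LS means at each visit will be reported to evaluate the within-patient treatment effect". The hypothesis is explicit: "The null hypothesis is that there is no treatment effect (no difference from Baseline values) over time". The level is 0.05 per test (Section 8.6: "Analysis of efficacy endpoints will be made using statistical tests each with a 2-sided" α of 0.05), and Section 7.1 adds "Confidence limits (CLs) will be 2-sided and calculated with a 95% confidence coefficient".

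The LS mean request is "lsmeans TRT01PN*AVISITN / cl". It has no AT option and Baseline is not centred. Section 8.6.2.2 says its NRS analysis is similar to that of Section 8.6.1. Section 8.6.3 repeats the form for plasma 5-HIAA: "model RESP = PLA5HIAA AVISITN / ddfm=kr".

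**The concern.** In a randomised comparison the point at which a baseline covariate is evaluated cancels out of the treatment difference. Here nothing cancels: the adjusted mean change is set against zero.

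Without an AT option, the software evaluates the LS mean at the mean of Baseline over the records used and treats that value as fixed. In fact it is estimated from the same patients, and its sampling error feeds into the mean change through the regression slope. The Kenward-Roger adjustment allows for estimated covariance parameters, not for an estimated covariate mean. Both the reported and the true variance fall as 1/n, so a larger sample does not remove the gap.

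There is also a smaller effect on the estimate. Missing data are not imputed (Section 7.3), and patients who stop before Week 84 are expected (note to file of 23 November 2015). Patients with more visits therefore weigh more in the Baseline mean.

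At stake are the confidence limits and p-values for the secondary objective (quality of life) and for the pharmacodynamic endpoint.

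**Working it through.** **Inputs from the SAP.** Two-sided α of 0.05 and 95% limits (Sections 7.1, 8.6); one group; change regressed on visit and Baseline with one common slope; up to 100 patients, no formal sample size calculation (Section 4.5).

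**Assumed, because the SAP gives no values.** Baseline-to-visit correlation r, the ratio k of follow-up SD to baseline SD, and drop-out.

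**Closed form, complete data.** Scale the baseline SD to 1. The LS mean at the sample mean Baseline equals the raw mean change.
- Slope of change on Baseline: rk − 1.
- Variance the model reports: k²(1 − r²)/n.
- True variance of the mean change: (1 + k² − 2rk)/n.
- Difference: (rk − 1)²/n, which is slope² × Var(Baseline)/n, the omitted term.
- Standard error ratio: q = √[k²(1 − r²)/(1 + k² − 2rk)]. For k = 1 this is √[(1 + r)/2].
- Actual size: 2[1 − Φ(1.96q)].

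Equal SDs (k = 1):

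| r | q | Actual size | Width needed, 1/q |
|---|---|---|---|
| 0.3 | 0.806 | 11.4% | 1.24 |
| 0.5 | 0.866 | 9.0% | 1.15 |
| 0.7 | 0.922 | 7.1% | 1.08 |
| 0.8 | 0.949 | 6.3% | 1.05 |
| 0.9 | 0.975 | 5.6% | 1.03 |

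Example, r = 0.5: model variance 0.75/n, true variance 1.00/n, q = √0.75 = 0.866, 1.96 × 0.866 = 1.70, two-sided tail 9.0%.

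Unequal SDs:
- k = 0.8: 16.5% at r = 0.3, 13.8% at 0.5, 12.1% at 0.7, 12.6% at 0.9.
- k = 1.25, r = 0.8: model variance 1.5625 × 0.36 = 0.5625; true variance 1 + 1.5625 − 2.0 = 0.5625. The slope is zero and the size is 5.0%.

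**Simulation, complete data (20,000 replicates, n = 100, k = 1).** For r of 0.3, 0.5 and 0.7 the size was 11.3%, 8.7% and 7.2%. Over r of 0.15 to 0.9 and n of 50, 80 and 100, adding the omitted term gave 4.5 to 5.1%, and a paired t-test gave 4.7 to 5.3%. This isolates the cause.

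**Four-visit REML fits, ARH(1) plus random intercept** (600 replicates, n = 50 and 100, drop-out 0 or 12% per visit, t with n − 2 degrees of freedom standing in for Kenward-Roger; Monte Carlo error about 1 point):
- constant r of 0.3, 0.5, 0.7: about 8 to 12%, 7 to 10% and 6 to 9%;
- correlation decaying over time: about 4 to 6% at Week 24 and 8 to 14% at Week 84.

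**Record weighting.** With drop-out depending on baseline (n = 80, r = 0.5), the LS mean shifted by about 0.07 SD and the tests ran at 11 to 14%. With drop-out depending on the last score (SD 20, 62 to 65% left at the last visit), in a simpler random-intercept model, the shift was 0.6 to 0.8 points on the 0 to 100 scale, that is 0.03 to 0.04 SD.

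**The case against.** The strongest reply is that an LS mean at a fixed covariate value is the ordinary reading of such a model, and that its limits are correct given the observed baselines. That is true. But the SAP does not state a conditional hypothesis. It states no difference from Baseline in the patients treated, and for that null the baseline mean is an estimate.

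Second, the size of the effect is not fixed by the document. A reader might infer that all these tests run at some rate such as 7 to 14%, or that every p-value is anti-conservative. The documents support neither. They give no correlation, SD or drop-out rate. Patients continue at the same dose without interruption, so high correlations are plausible, and then the size is about 6%. Symptoms may worsen with progression (Section 8.6), so a wider follow-up spread, with little or no inflation, cannot be excluded. Week 24 can be near nominal.

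Third, the code is labelled a sample, the evaluation point is a software default, and the code would not run as printed, because TRT01PN is in neither CLASS nor MODEL. The point therefore concerns the evidently intended LS means by visit. The SAP text also makes Baseline a covariate and reports LS means, so repairing that line alone would not change the standard error.

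Fourth, the consequence is limited. Safety is primary, efficacy is uncontrolled, and the descriptive n and SD of change let a reader compute an observed-case standard error. This bears on the weight of the point, not on its correctness.

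**Conclusion.** The point holds in qualified form. In Sections 8.6.1, 8.6.2.2 and 8.6.3 the planned standard error omits slope² × Var(Baseline)/n, and the 95% limits and 5% tests are generally too narrow and too liberal for the null the SAP states. They remain valid conditionally on the observed baselines.

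Under equal SDs and complete data the actual level is about 11%, 9% and 7% at correlations of 0.3, 0.5 and 0.7, and about 6% at 0.8 to 0.9. It is about 12 to 16% if the follow-up SD is 0.8 of the baseline SD (correlation 0.3 to 0.9). It returns to 5.0% at a ratio of 1.25 with correlation 0.8. These are assumed scenarios, not rates for this trial. The shift in the estimate from record weighting is slight. As the endpoints are secondary, this is a correction that should be made; it does not threaten the primary objective.

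**What to change.** For the tests of change from Baseline in the three sections:

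- Put the Day 1 value in the response vector, with AVISITN including Baseline Day 1 (the Section 8.6.1 text already starts the time effect there), and remove BASE or PLA5HIAA as a covariate.
- Use an unstructured within-patient covariance, drop the then redundant random intercept, and pre-state a fallback if the fit does not converge. Five occasions for EORTC (Day 1 plus four visits) mean 5 × 6/2 = 15 covariance parameters. Nine for 5-HIAA (Day 1, seven visits, follow-up) mean 9 × 10/2 = 45, so the fallback matters with up to 100 patients.
- Report visit-minus-Day-1 contrasts with Kenward-Roger limits.
- If the Baseline covariate is kept, evaluate at the patient-level mean Baseline and include the variance of that mean, as an added term or by patient-level bootstrap.
- Correct the LSMEANS statement, which names a variable that is not in the model.

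**Cost.** A code change and a rerun. Limits become wider, by about 8 to 24% for correlations of 0.7 to 0.3 with equal SDs. Interim outputs already exist (the note to file of 5 February 2016 gives 22 January 2016 for the Study 302 GI.NET21 outputs), so the change should be recorded as a dated SAP amendment with its reason, stating that open-label interim results had been seen.
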